 - b. Has previously demonstrated an inadequate response to or failed to tolerate corticosteroids or immunomodulators (ie, 6-MP, AZA, and MTX) but not a biologic, ie, the Bio-NF population (Appendix 3 of the Master protocol PLATFORMPACRD2001, Definitions of Inadequate Response to or Intolerance of Corticosteroids or AZA/6 MP and Corticosteroid Dependence)
9. Therapy for the treatment of Crohn's disease must include at least 1 of the following medications, which should have been maintained at stable doses prior to the baseline (Week 0) visit:
 - a. Oral 5-aminosalicylic acid (5-ASA) compounds
 - b. Oral corticosteroids at a prednisone-equivalent dose ≤ 25 mg/day, or 9 mg/day of budesonide, or 5 mg/day beclomethasone dipropionate
 - c. Antibiotics being used as a primary treatment of Crohn's disease
 - d. Conventional immunomodulators (ie, AZA, 6-MP, or MTX) if participants have been taking them for at least 12 weeks and have been at a stable dose for at least 4 weeks prior to baseline

Laboratory Parameters

10. Have screening laboratory test results within the following parameters:
 - a. Hemoglobin ≥ 8.0 g/dL

- b. White blood cell count (WBCs) $\geq 3.0 \times 10^3/\mu\text{L}$
- c. Neutrophils $\geq 1.5 \times 10^3/\mu\text{L}$
- d. Platelets $\geq 100 \times 10^3/\mu\text{L}$
- e. Serum creatinine $< 1.7 \text{ mg/dL}$
- f. Alanine aminotransferase (ALT) and aspartate aminotransferase (AST) concentrations must be within 2 times the upper limit of the normal range for the laboratory conducting the test
- g. Direct (conjugated) bilirubin $< 1.0 \text{ mg/dL}$

Pregnancy Testing

- 11. A woman of childbearing potential must have a negative highly sensitive serum (β -human chorionic gonadotropin [β -hCG]) pregnancy test result at screening and a negative urine pregnancy test result at Week 0.

Other

- 12. Must sign an informed consent form (ICF) indicating that he or she understands the purpose of, and procedures required for, the study and is willing to participate in the study
- 13. Must sign a separate ICF if he or she agrees to provide optional DNA samples for research (where local regulations permit). Refusal to give consent for the optional DNA research samples does not exclude a participant from participation in the study
- 14. Willing and able to adhere to the lifestyle restrictions specified in this protocol

JNJ-67864238 intervention cohort specific inclusion criteria start with the letter A and are listed below.

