## 5.6.3. Additional Safety Assessments

### 5.6.3.1. Clinical Laboratory Tests

Clinical laboratory tests will be displayed for the participants included in the safety analysis set. Clinical laboratory values are to be graded using National Cancer Institute Common Terminology Criteria for Adverse Events (NCI-CTCAE) version 5.0 (see [Table 3](#)). Descriptive statistics and graphical displays will be presented for chemistry and hematology at scheduled time points.

Change/percent change from baseline to time point will be summarized for chemistry, hematology, tests and displayed by intervention group.

- Summary of the observed values and changes from baseline over time through the final efficacy & safety visit for clinical laboratory parameters.
- Summary of maximum NCI-CTCAE toxicity grade for postbaseline laboratory values through Week 12 and through the final efficacy & safety visit for clinical laboratory parameters listed in [Table](#) . For toxicity grades, treatment emergent (TE) will be concluded if the postbaseline value is worse than the baseline value.
- Shift tables for selected clinical laboratory parameters (ALT, AST, alkaline phosphatase and total bilirubin) at Week 12.
- For abnormalities based on normal range and/or criteria: If the postbaseline value is above the upper limit and the baseline value is below the upper limit (eg, Normal or Low), then the postbaseline abnormality will be considered TE. The same applies to the postbaseline value being below the lower limit with the baseline value being above the lower limit (eg, Normal or High).
- If the baseline value is missing, a postbaseline abnormality will always be considered as TE.

Listings of participants with any abnormal postbaseline laboratory values of CTCAE grade  $\geq 2$  will also be provided.

The laboratory data to be summarized are as follows:

- **Hematology assessments:** hematocrit, hemoglobin, platelet count, total leukocytes and differential WBC count (neutrophils, lymphocytes, monocytes, eosinophils, and basophils)
- **Blood chemistry assessments:** ALT, AST, alkaline phosphatase, albumin, total and direct bilirubin, blood urea nitrogen, calcium, chloride, creatinine, phosphate, potassium, total protein, and sodium.

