The baseline value for a participant is the value closest to but prior to the first dose of study agent (Week 0). Change from baseline is defined to be the assessment at the postbaseline visit minus the assessment at baseline. Summaries of laboratory data will be completed using all the available laboratory data at the time point of interest without imputing missing data. Shift tables summarize the number of participants with low, normal, and high values (determined by the laboratory normal ranges) at the post baseline visit for each of the classifications of low, normal, and high at baseline.

Table 3: Grading Criteria for Clinical Laboratory Tests [CTCAE Version 5.0]

Table 3: Grading Criteria for Clinical Laboratory Tests [CTCAE Version 5.0]					
Hematology Tests		Criteria			
Test	Direction	1	2	3	4
Hemoglobin (g/dL)	Increase	>0 - 2	>2 - 4	>4	
Hemoglobin (g/dL)	Decrease	<LLN - 10.0	<10.0 - 8.0	<8.0	
Lymphocytes (/mm  )	Increase		>4000 - 20,000	>20,000	
Lymphocytes (/mm  )	Decrease	<LLN - 800	<800 - 500	<500 - 200	<200
Neutrophils (/mm  )	Decrease	<LLN - 1500	<1500 - 1000	<1000 - 500	<500
Platelets (/mm  )	Decrease	<LLN - 75,000	<75,000 - 50,000	<50,000 - 25,000	<25,000
Total WBC count (/mm  )	Increase			>100,000	
Total WBC count (/mm  )	Decrease	<LLN - 3000	<3000 - 2000	<2000 - 1000	<1000
Chemistry Tests		Criteria			
Test	Direction	1	2	3	4
ALT	Increase	>ULN - 3.0 x ULN if baseline was normal; 1.5 - 3.0 x baseline if baseline was abnormal	>3.0 - 5.0 x ULN if baseline was normal; >3.0 - 5.0 x baseline if baseline was abnormal	>5.0 - 20.0 x ULN if baseline was normal; >5.0 - 20.0 x baseline if baseline was abnormal	>20.0 x ULN if baseline was normal; >20.0 x baseline if baseline was abnormal
AST	Increase	>ULN - 3.0 x ULN if baseline was normal; 1.5 - 3.0 x baseline if baseline was abnormal	>3.0 - 5.0 x ULN if baseline was normal; >3.0 - 5.0 x baseline if baseline was abnormal	>5.0 - 20.0 x ULN if baseline was normal; >5.0 - 20.0 x baseline if baseline was abnormal	>20.0 x ULN if baseline was normal; >20.0 x baseline if baseline was abnormal
Albumin (g/L)	Decrease	≥30 - <LLN	≥20 - <30	<20	

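### As written, the SAP's rule for treatment-emergent toxicity grades compares laboratory values, so small within-grade fluctuation counts as emergent for tests graded on fixed cut-points

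*SAP*

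**What the plan says.** SAP 5.6.3.1 (Clinical Laboratory Tests) plans a "Summary of maximum NCI-CTCAE toxicity grade for postbaseline laboratory values through Week 12 and through the final efficacy & safety visit". The rule for emergence follows in the same bullet: "For toxicity grades, treatment emergent (TE) will be concluded if the postbaseline value is worse than the baseline value".

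Four other provisions bear on how that sentence is read:

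- The paragraph before Table 3 defines the term: "The baseline value for a participant is the value closest to but prior to the first dose of study agent (Week 0". That is a measurement.
- The separate rule for normal-range abnormalities requires a limit to be crossed: "If the postbaseline value is above the upper limit and the baseline value is below the upper limit", with the mirror rule for low values.
- Table 3 grades some tests on fixed cut-points. For hemoglobin decrease, Grade 1 runs from the lower limit of normal (LLN) down to 10.0 g/dL and Grade 2 from below 10.0 to 8.0 g/dL. ALT, AST, alkaline phosphatase and total bilirubin are graded relative to baseline when baseline is abnormal; for ALT and AST, Grade 1 is then "1.5 - 3.0 x baseline if baseline was abnormal".
- SAP Appendix 10 grades baseline measurements too, always on the range meant for a normal baseline.

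Protocol 5.1, criterion 10 ("Have screening laboratory test results within the following parameters") admits "Hemoglobin ≥ 8.0 g/dL".

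**The concern.** An emergence flag on a graded result should mark a participant whose category has become worse. A comparison of raw measurements needs no change of category. Any post-baseline result that is graded and slightly worse than a single baseline reading is enough, and ordinary variation produces that often.

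The entry criteria make this relevant. The hemoglobin limit permits Grade 1 or Grade 2 at baseline. The limits for white cells (3.0 x10³/µL) and neutrophils (1.5 x10³/µL) permit Grade 1.

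Safety is a secondary objective. If the emergent-grade table mostly reports pre-existing low counts plus noise, its rates are too high in both arms and the ratio between arms moves towards 1.

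**Working it through.** The plan states no rate or count for this flag, so there is no figure to reproduce. The check compares the two possible derivations.

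**1. Worked records, Table 3 hemoglobin decrease.**
- 10.6 to 10.5 g/dL: Grade 1 at both times. Value rule: emergent Grade 1. Grade rule: not emergent.
- 9.4 to 9.3 g/dL: Grade 2 at both times. Value rule: emergent Grade 2. Grade rule: not emergent.
- 9.4 to 9.4 g/dL: not worse, so not emergent under either rule.

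**2. Exact probability.** If a participant's results are continuous and exchangeable (no true change), the chance that at least one of k post-baseline results is worse than the single baseline result is k/(k+1). For k = 4 (Weeks 2, 4, 8, 12) this is 4/5 = 80%. For k = 5 (adding the final visit) it is 5/6 = 83%.

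**3. Simulation across an entering population.** Assumptions, none from the documents: hemoglobin mean 12.3 g/dL, between-person SD 1.5, LLN 12.0, results rounded to 0.1, no true change. Baseline is at least 8.0 g/dL (the entry limit) and k = 4. The value rule needs a post-baseline result that is Grade 1 or higher and lower than baseline. The grade rule needs a maximum post-baseline grade above the baseline grade.

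| Within-person SD (g/dL) | Graded baseline: value rule | Graded baseline: grade rule | All: value rule | All: grade rule |
|---|---|---|---|---|
| 0.4 | 71% | 11% | 41% | 16% |
| 0.6 | 69–70% | 18% | 46% | 25% |
| 0.8 | 68% | 25% | 51% | 33% |

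**4. Simulation for a Grade 1 baseline at a fixed true level** (within-person SD 0.2, 0.3 or 0.5; k = 4 or 5; LLN 12.0).
- Value rule: 73%–90%.
- Grade rule, true level 11.0 or 11.5 g/dL: 0%–9%.
- Grade rule, true level 10.5 g/dL, close to the Grade 2 limit: 1%, 13%–16% and 44%–52% for the three SDs.

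**5. Effect on the contrast between arms.** Take step 3 with SD 0.4 and an assumed true fall of 0.7 g/dL in one arm only. All-participant rates are 41% and 68% under the value rule, a difference of 27 points and a ratio of about 1.7. Under the grade rule they are about 16% and 44%, a difference of about 28 points and a ratio of about 2.7. The absolute difference is nearly the same; the ratio is compressed.

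**6. Tests graded relative to an abnormal baseline.** Assumed true level 1.6 x ULN, log-scale within-person SD 0.1, 0.2 or 0.3, k = 5. Some result exceeds baseline in about 83%, but a grade needs more:
- ALT/AST, at least 1.5 x baseline: 0.9%, 23% and 40%.
- Alkaline phosphatase, at least 2.0 x baseline: 0%, 2% and 13%.
- Total bilirubin is the exception. With an abnormal baseline, any rise above 1.0 x baseline is Grade 1.

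**7. Would a plain grade comparison be enough?** Take ALT of 1.8 x ULN at baseline, which the 2 x ULN entry limit allows. Appendix 10 grades it on the normal-baseline range: Grade 1. A rise to 5.2 x ULN is 5.2/1.8 = 2.9 x baseline, still Grade 1 on the abnormal-baseline range (1.5–3.0 x baseline). Grade 1 against Grade 1 is not emergent, although the result is above the 5 x ULN threshold in Protocol Appendix 4. The normal-range rule also misses it, because baseline was already high, and so does the Grade 2-or-higher listing. A plain grade comparison is therefore not enough for these tests.

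**The case against.** The best defence is that the sentence opens by referring to toxicity grades and sits in the bullet on maximum grade. Appendix 10 supplies a baseline grade, and the neighbouring normal-range rule works by category. A programmer could reasonably take value to mean graded value. Programming instructions are also in a separate Data Presentation Specifications document that is not available here. This stands as far as it goes: a grade reading is open. It does not settle the matter, because the section says toxicity grade where it means grade, defines the baseline value as a measurement, and nowhere excludes the comparison of measurements.

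Three stronger conclusions that a reader might draw are not supported:

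- *Participants with stable abnormalities are counted as new toxicity.* An unchanged result is not worse than baseline. The problem is small worsening within a grade.
- *Entry with ALT or AST up to 2 x ULN creates the same problem.* Table 3 requires at least 1.5 x an abnormal baseline before any grade is assigned, so small fluctuation gives no grade.
- *A real drug effect would be hidden.* The noise falls on both randomised arms, and the absolute difference in step 5 is almost unchanged. The SAP also plans maximum grades, values and changes by visit, listings of Grade 2 or higher, liver-test shift tables and the limit-crossing rule.

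It is also fair that the percentages depend on one analyte and assumed inputs, and that Appendix 10 makes toxicity-grade analyses conditional on need.

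**Conclusion.** The point holds in a limited form. As written, the rule counts within-grade fluctuation as treatment-emergent for fixed-cut-point tests, with hemoglobin the clearest case because entry permits Grade 1–2. On the population assumptions of step 3, about seven in ten participants with a graded baseline would be flagged with no drug effect, against 11%–25% under a grade comparison. The contrast narrows where true levels lie near a cut-point and within-person variation is large (step 4). The documents do not say how many participants will enter with graded values, so the trial-level count cannot be stated.

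The consequence is inflated emergent counts in both arms and a compressed relative contrast, without bias towards either arm. No efficacy analysis or decision rule uses the flag. Severity: minor correction to a safety summary.

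**What to change.** Replace the sentence in SAP 5.6.3.1 with:

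> For toxicity grades, TE will be concluded if the postbaseline toxicity grade is higher than the baseline toxicity grade. For tests that Table 3 grades relative to baseline when baseline is abnormal (ALT, AST, alkaline phosphatase, total bilirubin), any postbaseline grade of 1 or more in a participant with an abnormal baseline is TE, because that grade already measures worsening from baseline.

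The second sentence covers the case in step 7, which the present wording does flag and a plain grade comparison would lose. The missing-baseline rule ("If the baseline value is missing, a postbaseline abnormality will always be considered as TE") can stay as it is.

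One limit remains. Small bilirubin rises above an abnormal baseline will still count, because Table 3 itself starts Grade 1 just above 1.0 x baseline; a table footnote should say so.

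The cost is two sentences in the SAP and the matching derivation in the programming specifications. No new data are needed and the efficacy analysis is untouched.

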X^z Plasma JNJ-67864238 concentration ^t				X	X	X	X	X	X
X^z Serum antibodies to JNJ-67864238 ^t				X		X		X	X
X^{aa} Fecal samples for stool concentrations of JNJ-67864238 ^t					X	X	X	X	X
Pharmacodynamics/Biomarkers									
Whole blood samples for biomarkers ^t		X		X	X	X	X	X	X
Serum samples for biomarkers ^t		X		X	X	X	X	X	X
X^{aa} Fecal samples for biomarkers ^t		X ^p		X	X	X	X	X	X
Saliva samples for microbiome ^t				X				X	X

Table 1: Consolidated Schedule of Activities - PLATFORMPACRD2001 and 67864238PACRD2001											
67864238PACRD2001 specific events	Period	Screening ^a	Treatment Phase ^b					Early Termination ^c	Final Safety Follow-up ^d		
			Week	-5 weeks	0	2	4	8	12		
	Study Procedures										
	Pharmacogenomics (DNA)										
	Whole blood samples for DNA analysis ^u			X							

Abbreviations: CDAI=Crohn's Disease Activity Index; CRP=C-reactive protein; DNA=deoxyribonucleic acid; ECG=electrocardiogram; HBV=hepatitis B virus; HCV=hepatitis C virus; HIV=human immunodeficiency virus; NRS=numeric rating scale; PGIC= Patient's Global Impression of Change; PGIS= Patient's Global Impression of Severity; PROMIS=Patient-Reported Outcomes Measurement Information System; RNA=ribonucleic acid; TB=tuberculosis.

Footnotes:

- a. The screening period should be a minimum of 7 days to allow for collection of CDAI data. Participants who are rescreened do not need to have a minimum of 7 days, provided that they have enough data to support CDAI calculation. The screening period should be a maximum of 5 weeks.
- b. Visit windows should be \pm 4 days for each visit.
- c. A participant will not be automatically withdrawn if they discontinue the study intervention before the end of the intervention cohort. Participants should return for all scheduled visits including the final safety follow-up visit.
- d. All participants should complete a final safety follow-up visit after their last study intervention administration. The safety follow-up period after the last dose of the study intervention should be 4 weeks.
- e. Informed consents for both the Master protocol and the Intervention Specific Appendix must be signed before first study-related activity.
- f. Minimum criteria for the availability of documentation supporting the eligibility criteria are described in Source Documentation in Appendix 5 of the Master protocol PLATFORMPACRD2001, Regulatory, Ethical, and Study Oversight Considerations. Check clinical status again before first dose of study intervention.

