10.4. Appendix 4: Liver Safety: Suggested Actions and Follow-up Assessments

10.4.1. Stopping Algorithm

Study intervention will be discontinued for a participant if liver chemistry stopping criteria are met.

Phase 2 Liver Chemistry Stopping Criteria and Increased Monitoring Algorithm (no preexisting liver disease)

Abbreviations: ALT = alanine transaminase; AST = aspartate transaminase; INR = international normalized ratio; SAE = serious adverse event; ULN = upper limit of normal; Tbili = total bilirubin

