
 • A specialist or hepatology consultation is recommended 
If ALT or AST - $\geq 3 \times \text{ULN}$ AND total bilirubin $< 2 \times \text{ULN}$ and INR ≤ 1.5:
 
 • Repeat liver chemistry tests (include ALT, AST, ALP, total and direct bilirubin, and INR) and perform liver chemistry follow-up assessments within 24 to 72 hours • Monitor participants weekly until liver chemistry abnormalities resolve, stabilize, or return to baseline 
RESTART/RECHALLENGE
 
 • Do not restart/rechallenge participant with study intervention 	
 recreational drugs and other over-the-counter medications) • Record alcohol use on the substance use alcohol form 
If ALT or AST $\geq 3 \times \text{ULN}$ AND total bilirubin $\geq 2 \times \text{ULN}$ or INR > 1.5 (if measured) obtain the following in addition to the assessments listed above:
 
 • Anti-nuclear antibody, anti-smooth muscle antibody, Type 1 anti-liver kidney microsomal antibodies, and quantitative total immunoglobulin G (IgG) or gamma globulins • Serum acetaminophen adduct assay, when available, to assess potential acetaminophen contribution to liver injury in participants with definite or likely acetaminophen use in the preceding week • Liver imaging (ultrasound, magnetic resonance, or computerized tomography) and/or liver biopsy to evaluate liver disease; complete the medical encounter form • Liver biopsy may be considered and discussed with local specialist if available: 
 – In participants when serology raises the possibility of autoimmune hepatitis – In participants when suspected drug-induced liver injury progresses or fails to resolve on withdrawal of study intervention – In participants with acute or chronic atypical presentation • If liver biopsy conducted complete the medical encounter form
---	--

1. Serum bilirubin fractionation should be performed if testing is available. If serum bilirubin fractionation is not immediately available, discontinue study intervention if ALT $\geq 3 \times \text{ULN}$ and total bilirubin $\geq 2 \times \text{ULN}$. Additionally, if serum bilirubin fractionation testing is unavailable, **record the absence/presence of detectable urinary bilirubin on dipstick** which is indicative of direct bilirubin elevations suggesting liver injury.

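### The SAP's liver shift tables show only Week 12 low/normal/high classes, and ALT/AST peaks of 3×ULN or more can stay Grade 1 and unlisted when the baseline was raised

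*SAP*

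**What the plan says.** SAP 5.6.3.1 plans "Shift tables for selected clinical laboratory parameters (ALT, AST, alkaline phosphatase and total bilirubin) at Week 12". It then defines the classes: "Shift tables summarize the number of participants with low, normal, and high values (determined by the laboratory normal ranges) at the post baseline visit", set against the same three classes at baseline.

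Two other outputs in that section cover the whole post-baseline period. One is a summary of the maximum CTCAE grade, through Week 12 and through the final visit. The other is "Listings of participants with any abnormal postbaseline laboratory values of CTCAE grade" 2 or higher. SAP 5.6 adds by-arm descriptive statistics, including the maximum, for continuous safety variables.

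SAP Table 3 grades ALT and AST in two ways. From a normal baseline, Grade 2 is above 3.0 and up to 5.0×ULN. From an abnormal baseline, Grade 1 is "1.5 - 3.0 x baseline if baseline was abnormal", and Grade 2 starts above 3.0 times baseline.

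The protocol works in multiples of ULN:

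- **Entry** (5.1, criterion 10f): ALT and AST "concentrations must be within 2 times the upper limit of the normal range for the laboratory conducting the test".
- **Stopping** (10.4.2): ALT or AST at or above 5×ULN. At or above 3×ULN, drug also stops if total bilirubin is at least 2×ULN, INR exceeds 1.5, liver or hypersensitivity symptoms are present, weekly monitoring is impossible, or the elevation lasts at least 4 weeks.
- **After stopping**: "Study intervention will be discontinued for a participant if liver chemistry stopping criteria are met" (10.4.1) and "Do not restart/rechallenge participant with study intervention" (10.4.2), but "Participants should return for all scheduled visits including the final safety follow-up visit" (1.3, footnote c).

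SAP Appendix 8 and protocol 8.3.7 define a possible Hy's law case as ALT or AST ≥3×ULN with ALP <2×ULN, together with total bilirubin ≥2×ULN or INR >1.5 if measured. The SAP commits to summarising events of special interest only where needed.

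**The concern.** A participant whose transaminases peak at Week 4 and who then stops drug will usually still be seen at Week 12. The shift table may then show a recovered, off-drug value. If the enzymes were raised at entry and are still raised, it shows high at both times, whatever happened in between.

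The grade-based outputs are meant to catch the peak. For a raised baseline, however, they measure it against that baseline, while the protocol's liver rules use ULN. The two scales part company in the participants who start closest to the thresholds.

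At stake is the by-arm laboratory display in the first study of this drug in Crohn's disease: how many participants per arm reached 3×ULN, where weekly monitoring starts, or 5×ULN, where drug stops. Efficacy and the decision rules are not affected.

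**Working it through.** The plan states no figure on this point to reproduce. The check applies Table 3 to the protocol's thresholds.

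**Inputs.** Baseline ALT or AST of b×ULN, with 1 < b ≤ 2 (protocol 5.1, criterion 10f, taking the screening limit to hold at baseline). Table 3: Grade 1 from 1.5b to 3.0b. Protocol 10.4.2: thresholds at 3 and 5×ULN.

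**Step 1, normal baseline.** Any value above 3.0×ULN is Grade 2 or higher, so it is in the maximum-grade summary as such and in the listing. Only a value of exactly 3.0×ULN meets the protocol's threshold and stays Grade 1.

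**Step 2, abnormal baseline.** Since 1.5b ≤ 3.0 when b ≤ 2, every value from 3×ULN up to 3b×ULN is Grade 1. The share of the 3 to <5×ULN class that lies in Grade 1 is (min(3b, 5) − 3)/2. This is a share of the width of the class, not of participants.

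| Baseline b (×ULN) | Grade 1 upper limit 3b (×ULN) | Values ≥3×ULN that stay Grade 1 | Share of 3 to <5 class |
|---|---|---|---|
| 1.2 | 3.6 | 3.0–3.6 | 0.6/2 = 30% |
| 1.5 | 4.5 | 3.0–4.5 | 1.5/2 = 75% |
| 1.67 | 5.0 | 3.0–5.0 | 2.0/2 = 100% |
| 1.8 | 5.4 | 3.0–5.4 | 100% |
| 2.0 | 6.0 | 3.0–6.0 | 100% |

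The 5×ULN stopping limit falls inside Grade 1 only if 3b ≥ 5, that is b ≥ 1.67. The part at or above 5×ULN is 5.0–5.4 at b = 1.8 and 5.0–6.0 at b = 2.0.

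**Step 3, does the maximum grade at least rise?** SAP Appendix 10 grades baseline values on the normal-baseline scale, so 1.5×ULN at baseline is already Grade 1. A peak of 4.5×ULN is 4.5/1.5 = 3.0 times baseline, also Grade 1. The grade does not change.

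**Step 4, the joint criterion.** For total bilirubin with an abnormal baseline of c×ULN, Grade 1 runs to 1.5c. A value of 2×ULN is Grade 1 only if c ≥ 2/1.5 = 1.33; at c = 1.5 the range is 2.0–2.25×ULN. Entry restricts direct bilirubin but not total bilirubin.

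A constructed example: baseline ALT and total bilirubin both 1.5×ULN. Later, on one date, ALT is 4×ULN (4/1.5 = 2.67 times baseline, Grade 1), total bilirubin is 2.1×ULN (2.1/1.5 = 1.4 times baseline, Grade 1) and ALP is 1.0×ULN. This meets the SAP Appendix 8 definition with no Grade 2 liver value. INR has no row in Table 3, so a case qualifying through INR from a raised ALT or AST baseline could also go unlisted.

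**The case against.** **Other documents may hold these outputs.** The SAP places table titles, mock-ups and programming instructions in the DPS, and protocol 9.4.4 sends safety analyses to the Master protocol. This stands: a reader might infer that the whole plan lacks these displays, and the documents supplied cannot show that. The SAP does describe itself as the place for key derived variables, so a laboratory-derived Hy's law flag belongs there or needs a cross-reference.

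**The maximum-grade summary is already a worst-value output.** This also stands. A reader might conclude that participants at or above 3×ULN cannot be counted by arm at all. That goes too far. Every Grade 2 or higher ALT or AST exceeds 3×ULN, so the summary gives that count short only of values of exactly 3.0×ULN and the raised-baseline Grade 1 peaks.

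**Cases are captured elsewhere.** A reader might infer that liver signals would go undetected. They would not:

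- Protocol 8.2.4 has investigators review laboratory results and record clinically relevant changes as AEs.
- Stopping events need an AE form (10.4.2) and should reach the by-arm table of AEs leading to discontinuation (SAP 5.6.2).
- Possible Hy's law cases go on the special-interest form, and confirmed ones are SAEs (8.3.7).

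For an isolated, symptom-free value of 3 to <5×ULN that is monitored weekly and lasts under 4 weeks, recording as an AE depends on the investigator's judgement.

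**Direct bilirubin.** Protocol Appendix 4 counts at least a doubling of direct bilirubin in known Gilbert's syndrome, and drops the INR threshold for participants on anticoagulants. SAP Appendix 8 has neither provision. A missed direct-bilirubin case is therefore not a gap under the SAP's own definition.

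**Baseline-adjusted grading is a coherent, prespecified choice.** Agreed. The proposal adds to it and does not replace it.

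**Conclusion.** The point holds as a low-cost improvement to the by-arm laboratory display. In the SAP text, the liver shift tables can miss an on-treatment peak. The grade-based outputs recover every value above 3×ULN from a normal baseline. They do not separate or list values of exactly 3.0×ULN, or values from 3×ULN up to 3 times baseline in participants entering with ALT or AST above 1 and up to 2×ULN. By-arm laboratory counts at 3× and 5×ULN are incomplete for that subset.

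The size in participants is unknown, because the documents do not say how many of the planned 90 would enter with raised ALT, AST or bilirubin. The class-width shares in the table must not be read as proportions of participants. The conclusion rests on baseline values within the 2×ULN entry limit and on the SAP text alone.

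**What to change.** In SAP 5.6.3.1 keep the Week 12 shift table and add:

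1. Shift tables of baseline against worst post-baseline value, through Week 12 and through the final visit. ALT and AST in classes ≤1, >1 to <3, 3 to <5 and ≥5×ULN; total bilirubin and ALP in classes ≤1, >1 to <2 and ≥2×ULN.
2. A listing of participants with any post-baseline ALT or AST ≥3×ULN, whatever the CTCAE grade.
3. A count by arm and a listing, derived from laboratory data, of participants meeting possible Hy's law as SAP Appendix 8 defines it, with the INR limb applied where INR was measured. State before unblinding whether the values must come from the same date or from a set window.

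If the Gilbert's syndrome and anticoagulant provisions of protocol Appendix 4 are wanted, amend SAP Appendix 8 to match, so that the SAP holds one definition. Those two items would then have to come from medical history and concomitant medication records. If the DPS or the Master protocol already contains these outputs, a cross-reference is enough.

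The cost is SAP wording and standard outputs from data already collected. Worst-value tables will show more isolated, transient elevations in both arms. INR is not in the scheduled panel (protocol Appendix 5), so that limb will be incomplete.

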## **6.10. Appendix 10 Laboratory Toxicity Grading**

Laboratory Toxicity Grading related analysis will be performed as needed.

The grading scale use for lab assessments is based on ‘Common Terminology Criteria for Adverse Events (CTCAE) v5.0’.

If a laboratory value falls within the grading as specified below but also within the local laboratory normal limits, the value is considered to be normal and will be reset to grade 0.

Pre-baseline measurements will use the same grading ranges as applied to baseline measurements. In case a test has two sets of ranges – one for baseline normal and one for baseline abnormal, the one for baseline normal will be applied for all measurements taken pre-baseline and on baseline.

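### SAP Table 3 sets no upper-limit condition or reference point for the hemoglobin-increase grades, so a rise that is still below normal can be graded as toxicity

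*SAP*

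**What the plan says.** The hemoglobin-increase row of Table 3 in SAP 5.6.3.1 reads "Hemoglobin (g/dL) Increase >0 - 2 >2 - 4 >4". The decrease row beneath it is tied to the lower limit of normal: "Hemoglobin (g/dL) Decrease <LLN - 10.0 <10.0 - 8.0 <8.0". The other increase rows start at the upper limit of normal, at a multiple of an abnormal baseline, or at a high absolute count. Hemoglobin is the only one that starts at zero.

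SAP 6.10 (Appendix 10) adds one safeguard. A value that "falls within the grading as specified below but also within the local laboratory normal limits" is treated as normal and set back to grade 0.

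SAP 5.6.3.1 uses the grades in two outputs: a "Summary of maximum NCI-CTCAE toxicity grade for postbaseline laboratory values through Week 12" (and through the final visit), and "Listings of participants with any abnormal postbaseline laboratory values of CTCAE grade" 2 or higher. On treatment emergence it says: "For toxicity grades, treatment emergent (TE) will be concluded if the postbaseline value is worse than the baseline value".

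Anaemic participants can be enrolled. Criterion 10 in Protocol 5.1 asks only for "Hemoglobin ≥ 8.0 g/dL" at screening.

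**The concern.** A participant who enters anaemic and partly recovers has improved. The plan's own primary endpoint agrees, because the CDAI in SAP Attachment 3 adds points for a low hematocrit, so a rising hematocrit lowers the score. Under Table 3 as printed, the same recovery can receive a toxicity grade in the increase direction for as long as the value stays below the lower limit of normal. The 6.10 reset does not reach it.

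What is at stake is the meaning of one row of the laboratory safety tables. Its grade 1 count would be filled with small upward fluctuations in anaemic participants. A few entries in the grade 2 or higher listing would be recoveries rather than harms.

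**Working it through.** There is no figure in the plan to reproduce, so the check applies the printed rules to example values.

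**Inputs from the documents.** Increase cut-offs (0, 2 and 4 g/dL) and decrease cut-offs (lower limit, 10.0 and 8.0 g/dL) from Table 3; the reset from SAP 6.10; the entry floor of 8.0 g/dL from Protocol 5.1; change defined as post-baseline minus baseline in SAP 5.6.3.1; four post-baseline visits through Week 12 (Weeks 2, 4, 8 and 12).

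**Assumed.** The documents give no normal ranges. Lower limits of 11.5 to 13.5 g/dL and upper limits of 15.5 to 17.5 g/dL are used.

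**Step 1: which reading is usable.** As an absolute value, every out-of-range hemoglobin above 4 g/dL would be grade 3, which is unusable. As an excess over the upper limit, the row would work, but no SAP text says so. As a rise from baseline, it matches the SAP's own definition of change.

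**Step 2: apply it, with the 6.10 reset.**

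| Baseline to post-baseline (g/dL) | Rise | Increase grade as printed | Decrease grade, before to after | Increase grade with the fix |
|---|---|---|---|---|
| 8.0 to 8.5 | 0.5 | 1 | 2 to 2 | 0 |
| 9.0 to 11.0 | 2.0 | 1 | 2 to 1 | 0 |
| 8.5 to 11.0 | 2.5 | 2 | 2 to 1 | 0 |
| 8.2 to 12.4, lower limit 13 or 13.5 | 4.2 | 3 | 2 to 1 | 0 |
| 8.2 to 12.4, lower limit 11.5 or 12 | 4.2 | 0 (reset) | 2 to 0 | 0 |
| 14.0 to 14.5 | 0.5 | 0 (reset) | 0 to 0 | 0 |
| 16.0 to 18.0 | 2.0 | 1 | 0 to 0 | 1 |

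The first three rows hold at every assumed lower limit. With a baseline of at least 8.0, a grade 3 rise that is still below normal needs a lower limit above 8.0 + 4 = 12.0 g/dL. The last row shows that the fix still grades a rise above normal. At an upper limit of 15.5 the baseline already exceeds it, so the rise is 18.0 − 16.0 = 2.0, grade 1. At 16, 17 or 17.5 the excess is 2.0, 1.0 or 0.5, also grade 1.

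**Step 3: noise alone.** For a stable participant with exchangeable values, the chance that at least one of k post-baseline values exceeds baseline is k/(k + 1). For k = 4 this is 4/5 = 80%. If a fifth value is counted in the summary through the final visit, it is 5/6 = 83%. A simulation with true hemoglobin 10, lower limit 12 and within-person SD of 0.3 to 0.8 g/dL gives 79–80% and 83%. Ties from rounded laboratory values would lower these a little.

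**Step 4: across all participants (illustration, inputs assumed).** Half men; true hemoglobin with SD 1.5 around 14.0 (men) and 12.6 (women); lower limits 13.5 and 12.0; measurement SD 0.4 and visit SD 0.5, so combined √(0.16 + 0.25) = 0.64; about 36% below the lower limit at baseline; recovery building up over four visits.

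| Recovery (g/dL) | Share with increase grade 1 or higher while below normal |
|---|---|
| 0 | 25.6% |
| 0.5 | 26.2% |
| 1.0 | 25.5% |
| 2.0 | 22.7% |

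The share at grade 2 or higher rises over the same range, from about 0.5% to 2.7%. A separate run under similar inputs gave about 0.6% to 3%. In the active arm that is 54 × 0.005 = 0.3 to 54 × 0.03 = 1.6 participants.

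The grade 1 share depends mainly on how many participants are anaemic. With no recovery, about 70% to 80% of them would be graded. If 20%, 36% or 50% of participants are anaemic, that is about 14–16%, 25–29% or 35–40% of all participants.

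**The case against.** **The row may be shorthand.** The SAP says it grades by CTCAE version 5.0, and the printed row may abbreviate a criterion anchored in that source. The documents cannot settle this. Corrected calcium in the same table carries an asterisk with no visible note, so table notes may also be missing from the copy read. Both points are fair, but neither supplies a reference for hemoglobin. A programmer working from Table 3 and 6.10 would have none. If the anchored meaning was intended, the fix simply states it.

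**Treatment emergence.** A reader might infer that these rises are reported as treatment-emergent toxicities. The text does not go that far. The test is whether the post-baseline value is worse than baseline, with no direction given. Compared within the increase row (grade 0 to 1 or 2), the rise qualifies. Judged clinically, a move from 8.5 to 11.0 is not worse. The separate rule requiring a value above the upper limit covers abnormalities based on the normal range or criteria, and is stated apart from the toxicity-grade rule. On either reading, the value still enters the maximum-grade summary and, at grade 2 or higher, the listing.

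**Bias against an effective drug.** This is also tempting, and it is not supported at grade 1 or higher. Larger recoveries carry values into the normal range, where 6.10 resets them. The share is therefore flat and then falls; with an immediate recovery of 2.0 g/dL it drops to 10.7%. Only grade 2 or higher rises with recovery, and only slightly.

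**Consequence.** SAP 6.10 makes grading analyses as needed, and the change-from-baseline summaries would show the true direction. This limits the harm but does not correct the grade.

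**Conclusion.** The row is wrong as written, with minor consequences. Followed literally, it assigns an increase grade to a hemoglobin that has risen but is still below normal. The point does not extend to every rise, because one that ends inside the normal range is reset to grade 0.

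The main effect is an uninformative grade 1 count, since about four in five stable anaemic participants would be graded by fluctuation alone. The secondary effect is a small distortion at grade 2 or higher, about 0.5% to 3% of participants.

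The 4/5 figure needs only exchangeable values that stay below the lower limit. The percentages across all participants rest on assumed hemoglobin distributions, normal limits and anaemia prevalence, none of which the documents give. The conclusion also rests on reading the row as a rise from baseline. No endpoint, estimand, or success or futility rule uses these grades.

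**What to change.** In SAP Table 3, apply the hemoglobin-increase grades only when the post-baseline value is above the upper limit of normal. Measure the increase from that limit, or from baseline if baseline is already above it. In SAP 6.10, add that a value at or below the upper limit is grade 0 in the increase direction. For these below-normal values, the question of what counts as worse in the treatment-emergent rule then no longer arises.

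The cost is one table cell, one sentence and one programming condition, with no new data. The small downside is one more stated and programmed departure from the printed grading row, of the same kind as the existing 6.10 reset.
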